Short et al describes a quantifiable anatomical explanation for incomplete or failed anaesthesia from FNB or FICB in patients with #NOF. Several studies demonstrate that the FN block and FICB do not reliably block the obturator nerve or the lumbar plexus [16-22]. Distally, the high articular branches of the FN and AON are consistently located between the anterior inferior iliac spine and the iliopubic eminence [15]. The articular branches of the ON are located close to the inferomedial acetabulum. [15,23]. Subsequently the pericapsular nerve group block (PENGB) was designed to target the articular branches of the FN and AON by infiltrating the sub-psoas space at the level of the iliopubic eminence [23]. A case series of 5 consecutive patients with #NOF at Toronto Western Hospital was published in November 2018 and demonstrated the feasibility and efficacy of this block [23]. There is no published data describing the duration of analgesia provided by the PENG block.

The PENGB has subsequently been adopted by several practitioners at Lismore Base Hospital for the treatment of #NOF. We believe there is a study ongoing in peri-operative patients comparing PENGB to FICB in Toronto. We are not aware of any research into the utilisation of the PENGB in the emergency department setting. Searches of multiple study registries reveal no ongoing trials.

A retrospective study of patients that received regional anaesthesia for # NOF at LBH in the first 4 months of 2019 was performed. This data included 40 patients that received regional anaesthesia in ED, 6 of whom received a PENG block.

In this audit, patients' total opioid requirements from time of block to time of operation were recorded and converted to oral morphine equivalents using the ANZCA Faculty of Pain Opioid Calculator.

This audit found that patients receiving PENG blocks required fewer opioids pre operatively (mean = 22.67 mg) than did patients who did not receive a PENG block (FIB mean = 26.15 mg and FNB mean = 30.90 mg). Of note, patients receiving PENG blocks required fewer opioids in the 0-6 hours period immediately post block (mean = 3.00 mg) than did patients who did not receive a PENG block (FIB mean = 6.38 mg and FNB mean = 9.10). These results were not statistically significant ($p = 0.5$). The null hypothesis was retained. One adverse event relating to PENG blocks was documented in the records (failed block).

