Provides anaesthesia to the lateral femoral cutaneous nerve, which innervates the site of skin incision for surgical repair (in lateral approaches only)	Anaesthesia of only some of the nerve branches of the femoral nerve that supply the anterior hip capsule. No blockade of AON [15]. Unlikely to provide blockade of the obturator nerve.
Very low risk for direct neural damage due to remote injection points.	Prolonged onset due to distant injection point and slow spread.

PERICAPSULAR NERVE GROUP BLOCK

A preliminary audit at Lismore Base Hospital performed in May 2019, results show a trend toward reduced pain and morphine requirements n=6. The difference was not statistically significant.

ADVANTAGES	DISADVANTAGES
Utilises bony sonographic anatomy, therefore less variations in performance is expected.	Deeper site of infiltration requires higher technical skills.
Target site contains nerves branches that innervate the anterior hip capsule with greater frequency than FNB or FICB. Only technique that blocks the AON [15, 23]. Closer proximity to obturator nerve branches than other techniques [15]. Makes obturator blockade very likely..	Sonographic anatomy not familiar to emergency physicians. Requires re-training and experience in ultrasound guided needle techniques.
Targets small, distal purely sensory nerves [15, 23]. This should convey a faster onset and more complete blockade. Rapid onset is particularly valuable in the emergency department, where the patient is likely to be moved soon after the block is inserted.	Not well established clinical practice. Quality evidence not yet produced.
Infiltration site is distant from major vasculature, so LAST is less likely. It is distant to any motor nerves which eliminates the risk for major motor nerve damage.	

Aims and Objectives

1. To confirm that the PENGGB is a safe and effective intervention for analgesia of patients presenting to the emergency department with hip fractures.
2. To perform a prospective observational study to assess the PENGGB comparing analgesic efficacy vs current practice of FICB and FNB

Null hypothesis

The PENGGB provides comparable analgesia to patients with fractured neck of femur compared to the FNB and FICB.

Study Design

A prospective observational study.

Current Practice:

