All patients presenting to Lismore Base Hospital with fractured neck of femur (#NOF) are placed on the NOF pathway. The pathway suggests that patients on the NOF pathway should receive regional anaesthesia (nerve block) within 30 minutes of arriving at the Emergency Department. The nerve block performed will be determined by the treating clinician.

Inclusion and Exclusion Criteria

Inclusion Criteria

1. Adult patients (>18 years) presenting to Lismore Base Hospital Emergency Department with radiologically confirmed #NOF. The neck of femur fractures include:
 - a. Sub-capital fracture
 - b. Surgical neck fracture
 - c. Intertrochanteric fracture
 - d. Peritrochanteric fracture
2. The patient receives a nerve block for their fractured neck of femur in the Lismore Base Hospital Emergency Department
3. The nerve block may occur before or after the radiological confirmation of diagnosis

Exclusion Criteria:

1. Regional anaesthesia not provided in the Lismore Base Hospital Emergency Department
2. Allergy to amide local anaesthetics
3. Infection of the skin overlying at the overlying the site of potential nerve block
4. The patient has already received a nerve block for this fracture prior to arrival in at Lismore Base Hospital
5. Other reason at the discretion of clinician/s
6. Femoral shaft fracture

Block Standardisation

As this is an observational study, intervention is not dictated by the study, but is at the discretion of the treating physician. However, there have been efforts to standardise aspects of the care provided to improve the validity of this observational data.

In accordance with usual standards of practice:

- All nerve blocks are to be performed with ultrasound guidance. Needle tip and infiltration should be directly visualised with ultrasound.
- All nerve blocks are to be performed with continuous cardiac monitoring and intravenous access.

Nerve Block Kit:

To encourage standardisation of nerve blocks within hour department a nerve block kit is already in use. It contains:

- 80 mm x 21 gauge Pajunk SonoSpot needle (or alternative needle stocked by the department)
- 0.9% sodium chloride - 1 x 10mL vial
- 20 mL luer lock syringe
- 3 mL luer lock syringe
- Drawing up needle
- 25 gauge 38 mm or 23 gauge 35mm needle for local infiltration
- Dressing kit
- Chlorhexidine 2% in 70% ethanol skin prep solution (30 mL)
- Sterile ultrasound probe cover and gel

Standard Order Set:

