A standard order set [Appendix 1] has been built into FirstNet (the electronic medical record). This order set includes blood tests, radiography, referrals and analgesia. This “NOF order set” has been approved by the #NOF pathway working group and is available to all medical officers in the Emergency Department. The investigators will facilitate Medical Officers to add this order set to their ‘favourite’ orders.

Data To Be Collected

Regional Anaesthesia Provided

- Type of nerve block
- Content of nerve block
- Experience of practitioner

Patient Demographics

- # NOF Subtype
- Baseline characteristics: age, gender, comorbidities, social history, opioid use

Pain Scores

1. Visual Analogue Scale (VAS) [Appendix 6]
 - a. 100mm scale. Measured in 1mm increments. Converted to a score from zero to ten.
 - c. Measured at rest and on movement
2. Pain Assessment in Advanced Dementia (PAINAD) [Appendix 6]
 - a. Paper or electronic calculator
 - b. Scored zero to ten

Patients who are cognitively intact will have pain scores measured using the VAS, converted to score from zero to ten.

Patients who have a history of significant dementia or who clinically have significant cognitive impairment will have pain scored by a nurse or doctor using the pain assessment in advanced dementia (PAINAD) score, also zero to ten.

Subjective Observed Patient Comfort During Nursing Cares

- A binary measure of analgesia. Adequate or inadequate?

Opioid intake

- At baseline
- Pre-hospital
- In ED prior to regional analgesia
- After regional analgesia

Standard Documentation

Documentation that is recorded as a usual part of patient care

Nerve Block: Clinicians will be encouraged to document the placement of nerve block and its content in a standardised fashion within the patient's medical record, as is usual practice.

Pain Scores: Pain scores are recorded in the electronic medical record alongside vital signs. This is usual practice of nursing staff in the emergency department and on surgical wards. The utilisation of the VAS pain score is however, a departure from usual practice. Other pain scores such as the numerical pain scale and faces pain scale are previously / currently used by nursing staff at Lismore Base Hospital.

Analgesia Intake: Will be recorded in the electronic medical record. This is usual practice.

Additional Documentation

Documentation that is additional to usual practice, for the purpose of this study

Additional Paper Documentation:

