- ❑ Documentation on a paper form SPIED ED Data Form [Appendix 4] in the emergency department. This is additional to usual documentation and may be replaced by utilising Medical Surveys for data entry in the ED.
- ❑ Subjective Observed Patient Comfort During Nursing Score. May be completed in paper form [Appendix 7] or within Medical Surveys.

Data Governance

Data Storage:

The completed SPIED ED Data Form [Appendix 4] will be filed by clinicians in a folder within the Acute clinical area of the Emergency Department at Lismore Base Hospital. The SPIED ED Data Form will be the enrolment record.. Completed forms will be frequently collected by the investigators and stored securely with the ED Support Offices, which require swipe card access. This data will be stored for 5 years after the completion of data collection and then destroyed.

All other paper forms associated with the SPIED Study will form part of the patient's hospital record and will be treated accordingly.

Data Access:

- Investigators who are clinicians at Lismore Base Hospital have access to the patient's electronic medical records in the usual fashion as they would for day to day clinical work.
 - Investigators who access a patient's file for the purpose of data collection rather than clinical care, will create an electronic entry to document that they are accessing the file for the purposes of the SPIED study.
- In the event that any research funding is obtained, a research assistant may have access to Medical Surveys data and eMR as do the investigators.

Statistical Analysis

Primary Outcome:

Reduction in pain scores over the first 12 hours after nerve block. We will apply the following statistical tests:

- Student's t-test to compare the reduction in pain score of patients who receive a PENGGB compared to FNB and FICB
 - Subgroup analyses of the cognitively impaired and non-cognitively impaired population. These populations will have pain scored by the PAINAD and VAS respectively.
 - Subgroup analysis of FNB and FICB separately

Secondary Outcomes

- Onset of block. Defined as the time until the first pain score ≥ 1.5 less than the pre-block pain score.
 - T-test
- Subjective observed patient comfort during nursing cares
 - Chi Square test
- Patient Preference in the event of crossover
 - Chi Square test
- Rates of block failure. Defined as not achieving a reduction in pain score of $\geq 1.5 / 10$
 - Chi square test

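### The primary comparison of clinician-chosen blocks is an unadjusted t-test, although the likely confounders are collected; the size and direction of the resulting bias are unknown.

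*Protocol*

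**What the plan says.** The protocol's second aim is to carry out "a prospective observational study" comparing PENG with FNB and FICB. Block choice is outside the study's control. Under Current Practice: "The nerve block performed will be determined by the treating clinician". Under Block Standardisation: "intervention is not dictated by the study, but is at the discretion of the treating physician".

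The protocol also describes who gives PENG. The background states: "The PENGB has subsequently been adopted by several practitioners at Lismore Base Hospital". The table of PENG disadvantages says "Deeper site of infiltration requires higher technical skills".

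Data To Be Collected lists "Experience of practitioner", fracture subtype, and "Baseline characteristics: age, gender, comorbidities, social history, opioid use", together with opioid intake before hospital and in the ED before the block. A pre-block pain score is taken (Primary outcome section). Cognitively intact patients are scored by VAS and impaired patients by PAINAD.

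Under Statistical Analysis, the primary test is a Student's "t-test to compare the reduction in pain score of patients who receive a PENGGB compared to FNB and FICB". The only additions are subgroup analyses by cognitive status and by comparator block. No regression, matching, propensity method or other adjustment appears in the protocol.

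**The concern.** Without randomisation, a t-test estimates the block effect only if the groups are alike in whatever else drives pain reduction. The protocol gives reasons to expect that they are not:

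- **Operator.** PENG is in the hands of some practitioners and is said to need more skill, so block type and operator are plausibly linked.
- **Patient.** The FNB table says that standard femoral blocks are impractical where vascular disease with stents or prostheses distorts the anatomy. Comorbidity can therefore steer the choice.
- **Fracture.** Intertrochanteric and peritrochanteric fractures are eligible, while the rationale for PENG rests on the nerve supply of the anterior capsule. Subtype may affect both choice and response.
- **Starting pain.** A change score depends on where the patient starts, because those with more pain have further to fall.

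The conclusion on non-inferiority or superiority is at stake. The protocol expects the result either to increase uptake of PENG or to discourage clinicians from changing practice, and a comparison of self-selected groups without adjustment is a weak basis for both.

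**Working it through.** **Inputs from the protocol** (Sample size and statistical power; Duration of Data Collection): one-sided 0.05, power 0.80, SD 2.4, difference 1.5, allocation 1:2, 74 patients (25+49). For early termination: 125 patients with 41 PENG blocks, two-sided test, difference 1.3. The protocol gives no size of confounding, no pre/post correlation and no SD for PENG, so those below are assumptions.

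**1. The plan's own figures.** With 1:2 allocation the smaller arm is n = 1.5 × ((z₁ + z₂) × SD / difference)².

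- Minimum: 1.5 × (2.486 × 2.4 / 1.5)² = 23.7, so 24+48 = 72, within two of the stated 74. The standard error at 25+49 is 2.4 × √(1/25 + 1/49) = 0.590, and noncentral-t power is 0.81.
- Early termination: 1.5 × (2.802 × 2.4 / 1.3)² = 40.1, so 41+82 = 123, against 125. Power at 41+84 is 0.81.

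Both figures reproduce, and both rest on an unadjusted two-sample comparison.

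**2. Effect of a bias b (assumed).** A bias shifts the centre of the t statistic by b / SE; for b = 0.5 at 25+49 this is 0.5 / 0.590 = 0.85. The columns for 25+49 are one-sided: the error when PENG is truly worse by the full 1.5 and the bias favours it, and the power when there is no true difference and the bias runs against PENG. The last column is the two-sided error with no true difference.

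| b (points) | Error at margin, 25+49 | Power, 25+49 | Two-sided error, 41+84 |
|---|---|---|---|
| 0 | 0.05 | 0.81 | 0.05 |
| 0.3 | 0.13 | 0.64 | 0.10 |
| 0.5 | 0.21 | 0.51 | 0.19 |
| 1.0 | 0.51 | 0.21 | 0.58 |

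For the same bias, the larger sample gives a larger two-sided error than 25+49 would (at b = 0.5, 0.19 against 0.13). More patients do not cure it.

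**3. Where a bias of this size could come from (assumed).** A pre-block imbalance of d points biases the change score by d × (1 − slope of post- on pre-block pain). With d = 1.0 and slopes of 0.2 to 0.7, this is 0.8 to 0.3 points. Nothing in the protocol shows that such an imbalance exists.

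**4. What adjustment does to power.** With equal pre and post SDs and pre/post correlation r, baseline adjustment multiplies the change-score variance by (1 + r)/2. If the covariates predict block choice with R², the variance of the block effect is also multiplied by 1/(1 − R²). Power at 25+49 with SD = 2.4 × √[(1 + r) / (2(1 − R²))]:

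| r | R² 0.1 | R² 0.2 | R² 0.3 |
|---|---|---|---|
| 0.3 | 0.906 | 0.875 | 0.834 |
| 0.5 | 0.867 | 0.831 | 0.785 |
| 0.7 | 0.828 | 0.788 | 0.739 |

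The range is about 0.74 to 0.91, around the unadjusted 0.81. It leaves out any outcome variance explained by the other covariates, which would return some power.

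**The case against.** **It is observational, and a SAP may hold the details.** Covariate lists and adjusted sensitivity analyses are often left to a SAP, and the protocol says that a positive result should lead to a randomised trial. This stands as a reason not to complain of missing detail. It does not cover the point, because the protocol does not leave the primary method open: it names the t-test.

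**Comparability is partly handled.** The cognitive-status subgroups separate VAS from PAINAD, and ultrasound guidance, a block kit and an order set standardise care. True, but the subgroups do not adjust the overall comparison, and uniform care does not balance operators or patients between blocks.

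**Adjustment is no clear cure.** In non-randomised groups, change-score and baseline-adjusted analyses rest on different untestable assumptions, and measurement error in the baseline score leaves the adjusted estimate biased when group means differ. Experience is recorded as a covariate, but it is not operator identity; if a few operators give most PENG blocks, overlap may be poor and the model extrapolates. A scale indicator does not make VAS and PAINAD commensurate. All of this stands, and it limits what the adjusted result can claim.

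**Adjustment always gains precision.** A reader might infer this from the usual randomised-trial formula. That formula assumes that block is independent of the covariates, which is the very thing in doubt here. A gain is not assured.

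**Student's test is itself anti-conservative at 1:2.** A reader might infer this too. The protocol cites SDs of 2.2 and 2.4, both for comparator blocks, and none for PENG. Neither the size nor the direction of any such effect can be derived.

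**Conclusion.** The point holds. Block choice is discretionary, the protocol itself links PENG to certain practitioners and skill, and the primary analysis is fixed without adjustment although the relevant variables are collected. This is a badly fixed analysis, and correcting it is cheap.

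Its size can only be illustrated. Under the assumptions above, a 0.5-point bias, one third of the 1.5 margin, moves the one-sided error at 25+49 from 0.05 to 0.21, or power from 0.81 to 0.51, depending on direction.

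Two stronger readings are not supported. A reader might conclude that the t-test will favour PENG; the documents say nothing on direction, and no baseline imbalance is shown. A reader might also conclude that the sample size is wrong; it is right for its own inputs, and only the method of comparison is in question.

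**What to change.** Before outcome data are examined, replace the primary t-test with a prespecified linear model:

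- **Outcome:** the same pain outcome and time point that the t-test would use, stated explicitly, since scores are taken at 15, 30 and 60 minutes and then about hourly. With pre-block score in the model, analysing the reduction or the post-block score gives the same block coefficient.
- **Covariates:** block group plus a short fixed list: pre-block score, pain scale (cognitive status), fracture subtype, practitioner experience and pre-block opioid. Code them coarsely, because 25 PENG patients support only a few terms.
- **Inference:** robust standard errors.
- **Sensitivity:** the unadjusted change-score comparison by Welch's test.
- **Diagnostics and wording:** tabulate covariates by block, check overlap, above all in practitioner experience, and report the result as an adjusted association.

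The cost is a few lines of analysis text and little extra work, with no new data items. State the downsides in the plan: power at the minimum size may be above or below 0.81 (about 0.74 to 0.91 under the assumptions shown), experience stands in imperfectly for operator, and unmeasured confounding and baseline measurement error remain.

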This audit was unable to demonstrate that PENG, FIB or FNB use less preoperative opioid consumption from time to block to time of operation. These results suggest a possible association between PENG block and reduced opioid consumption. However, these results are not statistically significant and are limited by sample size. This audit demonstrates that a larger study is warranted to assess the effectiveness of PENG blocks in hip fractures.

Pain score documentation was not sufficiently reliable to inform power calculations for this observational study.

Comparison of Nerve Blocks

FEMORAL NERVE BLOCK

ADVANTAGES	DISADVANTAGES
Relatively superficial infiltration.	Close proximity of infiltration to the large femoral vessels can result in inadvertent vascular puncture [24]. This can result in haematoma [34] and increases the risk of LAST (local anaesthetic systemic toxicity) if inadvertent intravascular injection occurs.
Sonographic anatomy familiar to the emergency physician	Requires needle placement directly adjacent to a large motor nerve, which may aggravate the consequences of neural damage [1]. Despite ultrasound guidance the neural tissue is not always well contrasting which increases the risk of intraneural injection.
Direct visualisation of the Femoral Artery (guiding structure for FNB) is easy to achieve in most patients.	In patients with peripheral vascular disease and stents or prostheses of the Femoral artery, the usual anatomy of the Femoral nerve is heavily distorted and standard FNB are impractical.
Usually leads to a motor block of the Quadriceps group of the femur, which prevents spontaneous movement of the injured leg and reduces pain	Unpredictable clinical efficacy. Anaesthesia of only some of the nerve branches of the femoral nerve that supply the anterior hip capsule. No blockade of AON [15]. No blockade of the obturator nerve.

FASCIA ILIACA COMPARTMENT BLOCK

ADVANTAGES	DISADVANTAGES
Well established in clinical practice	Relies on a significant spread of injectate to nerves distant from the point of injection.
Superficial site of infiltration is distant from major vessels, reducing the risk of LAST syndrome or haematoma.	Likely it's efficacy is reliant upon femoral nerve blockade, which may be more reliably achieved by a femoral nerve block.

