1. SPIED Study Emergency Department Data Form [Appendix 4]
 - a. Emergency Department staff may choose to use this form in place of Medical Surveys should they prefer, or if there are logistical challenges encountered with Medical Surveys
2. Limb Observation Chart: [Appendix 6]
 - a. It is standard practice on the surgical ward for nursing staff to complete limb observations every 1-2 hours on patients with #NOF and record these on a limb observation chart.
 - b. This chart has been modified for the SPIED study to also record pain scores
 - c. Also includes pain score calculators for the VAS and PAINAD
3. Subjective Observed Patient Comfort During Nursing Cares [Appendix 7]

Primary outcome = reduction of pain score

VAS pain scores will be recorded at rest and on movement. Movement is defined as attempted hip flexion to 15 degrees. PAINAD scores will be single measure based on nursing observation.

This score will be documented at the following times:

- Prior to placement of nerve block in the emergency department
- 15, 30, 60 minutes post placement of block
- With routine limb observations on the surgical inpatient ward, approximately hourly

Data will be collected for 12 hours post nerve block (or the next documented score after 12 hours) or until the patient is moved to the operating room, whichever is sooner.

Sample size and statistical power

The rationale for sample size calculations:

- A reduction in visual analogue pain score of 13 mm (1.3/10) was established as being clinically significant by Todd et al in 1996 [26].
- A clinically significant difference between two treatments that reduce pain scores by 1.3/10 has not been well defined
- Cooper et al used 1.5/10 difference in pain scores as a definition of clinically significant difference between blocks [27].
- Newman et al found a standard deviation in pain score reduction of 2.4 in patients receiving regional analgesia for #NOF in 2013 [28]. This figure was used by Cooper et al for their power calculation in 2018.
- Cooper et al found standard deviations of 2.2 and 2.4 respectively for the FNB and FICB [27].
- A retrospective study of patients that received regional anaesthesia for # NOF at LBH in the first 4 months of 2019 was performed by co-investigators of this study. This data included 40 patients that received regional anaesthesia in ED, 6 of whom received a PENG block. Pain score documentation was not sufficiently reliable to inform power calculations for this observational study.

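### Block content is recorded but enters no test, so if the local anaesthetic differs by block type the pain-reduction, onset and duration contrasts describe the block as delivered, not the block type alone

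*Protocol*

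**What the plan says.** The study is observational. Under Block Standardisation the protocol states that "intervention is not dictated by the study, but is at the discretion of the treating physician", and under Current Practice that the clinician decides which block is given. It adds that "there have been efforts to standardise aspects of the care provided to improve the validity of this observational data". The measures listed are ultrasound guidance, cardiac monitoring with venous access, a nerve block kit, and an electronic order set. The kit list includes one 20 mL syringe and a 10 mL saline vial but no local anaesthetic. The text shown names no agent, concentration or volume.

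Data To Be Collected includes "Content of nerve block" and the experience of the practitioner. Clinicians are encouraged, not required, to document content in a standard way.

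Statistical Analysis fixes a Student's "t-test to compare the reduction in pain score of patients who receive a PENGGB compared to FNB and FICB", t-tests for onset and duration, and chi-square tests for the remaining listed outcomes. The only subgroups are cognitive status and FNB and FICB taken separately. The second aim is to "assess the PENGGB comparing analgesic efficacy vs current practice of FICB and FNB". On follow-up: "Data will be collected for 12 hours post nerve block (or the next documented score after 12 hours"), or until the patient goes to the operating room if that is sooner.

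**The concern.** Without randomisation, nothing balances the injected drug across block types. If PENG operators tend to use a different agent from FNB and FICB operators, the difference in drug passes unadjusted into the difference in pain reduction, onset and duration. The protocol gives some reason to expect separate operator groups: PENG has been taken up by several practitioners, and its table of disadvantages says "Deeper site of infiltration requires higher technical skills". That makes different drug habits plausible; it does not show them.

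The protocol attributes expected PENG benefits, including faster onset, to the nerves targeted. It also expects the results to increase uptake or discourage change. A reader of a positive or non-inferior result will want to know whether it holds when the drug is the same. The stated tests cannot answer that, although the relevant variable is collected.

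A second weakness affects the onset and duration t-tests whatever the drug. Observation stops at about 12 hours or at theatre, so some patients will have no observed onset or no observed end of block. A t-test has no natural place for them.

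**Working it through.** **1. The plan's own figures reproduce.** Inputs from Sample size and statistical power: SD 2.4, difference 1.5, one-sided 0.05, ratio 1:2, total 74 (25+49). The early-termination rule gives 125 patients with 41 PENG blocks, two-sided, for a difference of 1.3.
- SE at 25 vs 49 = 2.4 × √(1/25 + 1/49) = 0.590; noncentral-t power for 1.5 = 0.809.
- SE at 41 vs 84 = 2.4 × √(1/41 + 1/84) = 0.457; noncentral-t power for 1.3 = 0.805.

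The planned sizes are not in dispute.

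**2. How far a same-drug contrast would shift.** Shift = (difference in agent share between groups) × (agent effect on pain reduction). The documents give neither factor. Both are assumed here:
- Shares 90% vs 50%, effect 0.5 to 1.0 points: 0.4 × (0.5 to 1.0) = 0.2 to 0.4.
- Shares 70% vs 50%, same effects: 0.2 × (0.5 to 1.0) = 0.1 to 0.2.
- Against the planning difference: 0.1/1.5 = 7%; 0.4/1.5 = 27%.
- Equal shares: zero.

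**3. What such shifts would do to error and power**, by noncentral t. The 5% error is taken at the null boundary, with the 1.5 read as the non-inferiority margin at 25 vs 49. These figures apply only if the target is a same-drug comparison.

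| Shift | 25 vs 49, one-sided error (shift towards PENG) | 25 vs 49, power (shift against PENG) | 41 vs 84, two-sided error | 41 vs 84, power (shift against PENG) |
|---|---|---|---|---|
| 0 | 0.050 | 0.809 | 0.050 | 0.805 |
| 0.1 | 0.070 | 0.760 | 0.055 | 0.740 |
| 0.2 | 0.095 | 0.705 | 0.072 | 0.665 |
| 0.4 | 0.165 | 0.580 | 0.140 | 0.497 |

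**4. Precision cost of adjusting for agent at 25 vs 49.** Adjusted SE = SE × √(1/(1 − φ²)), where φ is the correlation of block type with agent.

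| Assumed share, PENG vs comparator | φ | 1/(1 − φ²) | SE | Power for 1.5 |
|---|---|---|---|---|
| 70% vs 50% | 0.191 | 1.038 | 0.601 | 0.796 |
| 90% vs 50% | 0.393 | 1.183 | 0.641 | 0.749 |
| 50% vs 90% | −0.446 | 1.248 | 0.659 | 0.729 |

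The increase in SE runs from 0.601/0.590 (2%) to 0.659/0.590 (12%).

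**5. Why duration needs a rule for unfinished blocks.** Assume two agents lasting 8 h and 16 h, the longer one used in 90% vs 50%, and no effect of block type.
- If only observed ends enter the t-test, every observed end is at 8 h and the difference is 0.
- If unfinished blocks are scored at 12 h, the difference is 0.4 × (12 − 8) = 1.6 h.

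The same data give 0 or 1.6 h depending on a choice the protocol does not state.

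**The case against.** The strongest reply is that the second aim compares PENG with current practice, and drug choice is part of practice. For that target, a drug difference belongs to the contrast and is not a bias. This stands: the primary t-test is valid for blocks as delivered, and the error and power figures above describe a same-drug comparison that the protocol never names as its target.

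It is also fair that no imbalance is shown. Discretion over the drug is inferred from the general statement about the intervention and from the absence of a named agent. Appendices 1 and 4 are not shown and might steer the agent, and the exclusion for allergy to amide anaesthetics suggests a single drug class. A reader might infer that agents do differ, or that the planned test carries a real error rate of up to 17%. The documents support neither.

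Agent is one of several recorded factors left out of the tests. Operator experience, fracture subtype, comorbidities and opioid use are others. An agent-only model would remain confounded, so agent should enter alongside other recorded factors.

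Lastly, supportive models are commonly left to a SAP. That limits the weight of the point but does not remove it: this protocol has its own analysis section, and it fixes unadjusted tests by block name, including t-tests for outcomes cut off at 12 hours or theatre. The handling of unfinished blocks is indeed a separate matter from the drug, and it should be corrected on its own merits.

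**Conclusion.** The concern holds in a limited form. Block choice is not randomised, the text shown fixes no agent, and recorded content enters no test. If agent differs by block type, the pain-reduction, onset and duration contrasts describe the block as delivered and cannot be attributed to block type alone.

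The size cannot be derived from the document. The 0.1 to 0.4 point range rests wholly on the assumed shares and effects. The primary comparison and the sample size need no change. This is a worthwhile, inexpensive improvement with medium confidence, not a flaw that invalidates the plan. The case for time-to-event methods for onset and duration is independent of the drug, because it follows from the fixed end of observation.

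**What to change.** - Keep the primary t-test and label its result as block as delivered.
- Tabulate agent by block type, with concentration and volume where recorded.
- Add one supportive regression of pain reduction on block type, adjusted for agent together with other recorded factors such as operator experience. Leave volume and total dose out of this model: the protocol says of FICB "Relies on a significant spread of injectate to nerves distant from the point of injection", so volume may be part of the technique.
- If agent differs materially or does not overlap between groups, limit conclusions to the block as delivered.
- Replace the onset and duration t-tests with time-to-event analyses. Censor patients without an observed onset or end of block at the last score, 12 hours or theatre.

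**Cost.** Agent should be available from the existing content item, though whether concentration and volume are captured cannot be seen. The extra analysis work is small. Precision falls only in the supportive model: SE is about 2% to 12% larger for agent under the assumed shares, and further covariates would add their own cost, not computed here. The result depends on how completely content is documented, and the model cannot help if agent and block type coincide. Even with overlap, confounding from non-randomised block choice remains, so a difference should not be credited to the injection site.
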